## 7 STUDY SCHEDULE & PROCEDURES

Study eligible patients who are considered as candidates for sarecycline treatment as part of usual care Acne management will be screened, consented and recruited into the study, followed for up to 12 weeks post-index date, encompassing four distinct data collection encounters. With 'T' being the index date of sarecycline treatment initiation, the baseline data collection may transpire anytime between T= -2 weeks post-index date and T= +4 days post-index date; the 4-week follow-up data collection will happen at T=4 weeks post-index date  $\pm$  4 days; the 8-week follow-up data collection will happen at T=8 weeks post-index date  $\pm$  4 days, and 12-week follow-up data collection will happen at T=12 weeks post-index date  $\pm$  4 days. Index date is the date of initiation of sarecycline treatment, when the subject took the first sarecycline dose.

Different data elements will be collected from Site Investigators and from study Subjects at these data collection encounters, as outlined below. For patients of age 12yrs and older, acne patients themselves will complete relevant PRO elements pertinent to study endpoints, at all encounters; for patients of age 9-11yrs, parents/caregivers of pediatric patients will complete the PRO elements at all encounters, serving as a proxy, upon consulting with their child on question responses.

The schedule of events is summarized in Appendix A.

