## 7.3 First Follow-up Encounter (Encounter # 2)

At the completion of 4 weeks ( $\pm$  4 days) post-index date, the Site Investigator and Subjects will be asked to complete the first follow-up data collection, conducted via in-person or virtual/remote visits.

The patients will be advised to visit their site/clinician's offices to do the following:

- Drop off the first tablet/pill bottle of Seysara® (bottle # 1) supplied to them at study start, be it empty or with left-over pills.
  - This may be done as curb-side interaction, without entering clinician's offices.
- Pick-up the second bottle of Seysara® supply (bottle # 2) for the next four weeks of use.
  - This may be done as curb-side interaction, without entering clinician's offices.
- Undergo AV clinical evaluation inside clinician's office, if feasible.

The Site Investigators will complete the following, based on the information documented in patient medical charts and per clinical judgment guided by observing study subject via in-person or virtual/remote visit:

- IGA of current AV severity on the face.
- Patient treatment compliance, per sarecycline pill/tablets left over in the subject-returned bottle.

- Modifications to sarecycline treatment characteristics (e.g., change in dose, discontinuation), in the past 4 weeks, if any.
- AEs (incl. SAEs) related to or possibly related to sarecycline, observed in the past 4 weeks, as documented in the medical charts.
- Information on withdrawal from study (if occurred within the past 4 weeks).

The study Subjects will provide the following information via online survey portal or a mobile app: perceptions of current AV-related signs/severity. In case of pediatric patients, this information will be obtained from parents/caregivers as well.

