### **8.6.2 Documentation and Reporting of ADRs, Events with Fatal Outcome and Other Reportable Events**

The Site Investigator is responsible for assessing and documenting (in subject medical charts, as part of usual care) all AEs that occur at any time during the study. The Site Investigator will determine the relatedness, seriousness, and severity for each AE, which is then recorded in the

---

Adverse Events page of the eDCF, per study schedule of events (Appendix A). Following each subject encounter (be it, via in-person or remote encounters), the Site Investigator will evaluate the last 4-weeks of documentation (in subject medical charts) to report AEs and indicate whether those events resulted in stoppage or changes to dose of study medication.

Each AE that meets the definition of ADR will be recorded in the Adverse Events page of the eDCF and comprehensively documented on the “Adverse Drug Reaction” form to be reported within 1 working day (24 hours) of learning of the event and proactively reported to the Almirall LLC, CRO Safety Team via email or fax. ADR reporting details will be included in the Safety Reporting Plan.

For the purpose of this study, all AEs that meet the aforementioned definition of an SAE (in Section 8.6.1) that occurred during the treatment period will be reported to the sponsor as SAEs. Upon receipt of SAE data by the study CRO (collected as part of eDCF), they will be reported within 1 working day (24 hours) of learning of the event to the sponsor regardless of its relationship to the study treatment. If any additional information is needed to adequately document the SAEs, the study CRO will follow-up with the Site Investigators to ensure data completeness and will report the updated information back to the study sponsor. If an SAE results in modification of study medication dose or discontinuation of study medication and/or withdrawal of subject from the study, such information will be documented as part of eDCF and reported to the study sponsor.

As part of usual care, Site Investigator will follow Subjects concerning all SAEs and ADRs until adequate resolution or stabilization. If the SAE/ADR has not resolved or stabilized by the time the subject completed the final study visit, the Site Investigator may gather the status of the subject’s SAE/ADR within 30 days beyond the subject’s final study visit, if required.

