## 17.1 APPENDIX A: Study Schedule of Events

Study Encounter (physical or virtual)	Baseline E1	E2	E3	End of Study E4	Early Termination Visit
Week †		Wk 4 (± 4 d)	Wk 8 (± 4 d)	Wk 12 (± 4 d)	-
Informed consent	X				
Selection criteria	X				
Demographics & baseline clinical characteristics 	X				
Physical examination 	X			X	X
AV medical history and relevant comorbidites 	X			X	X
Seysara dose 	X	X	X	X	X
Dispensing and return of study medication	X	X	X	X	X
Prior acne medication (since diagnosis & past 6 months)	X				
Concomitant general medication	X			X	X
Concomitant anti acne medication	X			X	X
Site Investigator's clinical assessment of acne 	X	X	X	X	X
Study subject questionnaires 	X	X	X	X	X
AEs/SAEs 	X	X	X	X	X
Reasons for premature study withdrawal					X

† Expected in-person or virtual encounter/visit schedule, in relation to the index date (date of first administration of sarecycline).

 Clinical characteristics data assessed retrospectively based on what is documented in patient medical charts.

 Routine physical examination conducted as part of usual care alone and as documented in patient medical charts; such data may include - blood pressure, waist circumference, height/weight measurements.

 May include AV date of diagnosis, baseline severity, relevant comorbidities, per clinician judgment and/or as documented in patient medical charts immediately before the index date; new emerging comorbidities during the study period will be recorded, based on the documentation in patient medical charts.

 Expected usage is once daily, every day during the duration of the trial.

 Site Investigator assessments of AV severity of Subjects may be conducted during subject visit to clinician offices, or via remote/virtual (telehealth) visits owing to Covid-related travel restrictions.

 Subject self-assessments will include PtGA of acne severity; various HRQOL assessments will be conducted at baseline and Week 12.

 In the case of premature study discontinuation due to an AE, the Investigator should make every effort to collect the AE duration and outcome. Any SAE that is ongoing at the End of the Study or at the time of premature withdrawal will be followed up until the SAE is resolved or at least up to 4 weeks. AE follow-up information will be reported in the eDCF.

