## 2.2 Study End Points

The primary endpoint of the study will be the PROs, in terms of self-perceived acne symptoms and impact of acne on emotional functioning, social functioning and activities of daily living, at Week 12.

The secondary endpoint will be the proportion of Subjects with Facial IGA success at Week 12, defined as a 2-point decrease in IGA score from baseline and a score of 0 (clear) or 1 (almost clear).

Additional endpoints of the study will include:

- Proportion of Subjects for whom Site Investigator reported 'very satisfied' or 'satisfied' in the question on global satisfaction with sarecycline treatment, at Week 12.
- Description of changes in PROs from baseline, at Week 12.
- Frequency of documented adverse events (AEs) and severe adverse events (SAEs) during the 12-week study observation period.
- Comparison of Subject perception and Site Investigator perception of AV severity, at Week 12.

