### 6.6.2 Treatment Compliance

Compliance will be assessed by comparing the expected number of tablets taken, based on the total number of treatment days between the encounters/surveys, with the number of used tablets identified/returned at each encounter/visit.

- The number of tablets expected to be taken/used for a specific treatment period between study encounters is calculated based on the number of treatment days in that period; if the

number of days is greater than 30, it will be set to 30, corresponding to the # of tablets in a single Seysara® bottle supplied to subjects during each study encounter/visit.

- The number of pills used for a specific treatment period between study encounters is calculated as a difference between 30 (maximum # of tablets in a Seysara® bottle dispensed for each study encounter) and # of unused/returned pills (by subject) at the following study encounter.

Compliance (%) for a given treatment/encounter period =  
[# of pills expected to be used - # of pills unused] \* 100 / [# of pills expected to be used]

Treatment compliance will be calculated for each subject/visit and over all study encounters/visits for the Safety population, as indicated above. For the overall compliance for each subject, average (mean) of % compliance at individual subject encounters/visits will be calculated.

Compliance values that are less than 0% will be set to 0%, and compliance values that are greater than 100% will be set to 100%. For Subjects with missing data, no missing data imputation will be performed, and the compliance statistics will be computed using non-missing values for the study cohort at relevant study timepoints.

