## 6.10 Significant Protocol Deviations

A protocol deviation is defined as any intentional or unintentional failure to follow the requirements and procedures described in the study protocol. Deviations may have occurred at the subject level or at the site level, and could have been recorded by the site, or uncovered data review. Considering the real-world study design of PROSES, reflecting the routine clinical practices in the U.S and associated patient encounters and routine/standard of care data documentation, patients are expected to miss clinic visits or reschedule planned visits as life situations change. These will not be considered as protocol deviations.

Significant protocol deviations will be flagged, and these are defined as study-related issues that were likely to result in: significant impairment of the rights, welfare or safety of subjects; misconduct and/or fraud; and significant impairment of the integrity/validity of study results. Significant protocol deviations also include issues that were likely to impair monitoring and oversight of the study.

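### The scheduled review of AEs and dose changes looks back a fixed 4 weeks, but encounters can be up to 36 days apart or missed, so entries charted in the gap fall outside every scheduled review.

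*Protocol*

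**What the plan says.** Protocol 8.6.2 describes the review that follows each encounter: "the Site Investigator will evaluate the last 4-weeks of documentation (in subject medical charts) to report AEs", together with whether those events led to stopping or changing the dose. Protocol 7.3 lists AEs "observed in the past 4 weeks, as documented in the medical charts" and "Modifications to sarecycline treatment characteristics (e.g., change in dose, discontinuation), in the past 4 weeks, if any", and puts the same limit on withdrawal information. Sections 7.4 and 7.5 repeat these items for Weeks 8 and 12.

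Protocol 7 sets the timing. For example, "the 8-week follow-up data collection will happen at T=8 weeks post-index date", with 4 days allowed either side; Weeks 4 and 12 have the same window (also Appendix A). SAP 6.10 adds that "patients are expected to miss clinic visits or reschedule planned visits as life situations change" and does not class this as a protocol deviation. SAP 6.6.2 itself provides for long intervals: for expected tablets, if the "number of days is greater than 30, it will be set to 30".

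The safety endpoint in SAP 2.2 is the frequency of AEs and "severe adverse events (SAEs) during the 12-week study observation period". The footnotes to the AE and ADR tables in SAP 7.4.4 count events from first dose until 30 days after last dose, without a break. Protocol 5 intends every dose modification in the observation period to be captured.

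**The concern.** The reporting period is continuous, but the scheduled collection behind it is a series of 28-day windows anchored on whenever the encounter happens. If an interval is longer than 28 days, its first days are in no window. Nothing in either document extends the look-back to the previous encounter or triggers a catch-up review after a missed one. A site that follows the text exactly can leave a charted AE or an interim dose change out of the eDCF, while the tables still present the result as a frequency over the whole period.

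The reverse happens when encounters are close together. Two look-backs then cover the same days, and one event can be entered twice. The event-level tables (SAP Tables 7.4.4.6 to 7.4.4.8, 7.4.4.10 and 7.4.4.11) count each occurrence but state no rule for recognising a duplicate entry.

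**Working it through.** The plan gives no coverage figure, so there is nothing of its own to reproduce.

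**Inputs**
- Look-back: 4 weeks = 28 days (Protocol 8.6.2, 7.3 to 7.5).
- Encounter days after the index date (day 0, not counted): V1 = 24 to 32, V2 = 52 to 60, V3 = 80 to 88 (Protocol 7 and Appendix A).
- Supply: 30 tablets per bottle (SAP 6.6.2). Use: "Expected usage is once daily, every day during the duration of the trial" (Appendix A).
- Each look-back covers the 28 days up to and including the encounter day.

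**Formulas**
- Uncovered days = max(0, V1 − 28) + max(0, V2 − V1 − 28) + max(0, V3 − V2 − 28).
- Overlap days = max(0, 28 − (V2 − V1)) + max(0, 28 − (V3 − V2)).

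**All three encounters attended in window**
- Exact timing (28, 56, 84): 0 + 0 + 0 = 0 uncovered.
- Longest interval: 60 − 24 = 36, or 88 − 52 = 36. Uncovered: 36 − 28 = 8 days.
- Week 4 encounter on day 32: 32 − 28 = 4, so days 1 to 4 are uncovered.
- Largest total over the 9 × 9 × 9 = 729 whole-day combinations: days 32, 52 and 88, giving 4 + 0 + 8 = 12 (days 1 to 4 and 53 to 60).
- Shortest interval: 52 − 32 = 20, an overlap of 28 − 20 = 8 days. The total over both intervals also cannot exceed 8. If both are 28 days or shorter, the total is 56 − (V3 − V1), at most 56 − 48 = 8. If one is longer, only the other contributes.

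**Encounters missed**

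| Missed | Uncovered, nominal timing | Range over the windows |
|---|---|---|
| Week 8 | 84 − 28 − 28 = 28 (days 29 to 56) | 24 to 36 |
| Week 4 | 56 − 28 = 28 (days 1 to 28) | 24 to 32 |
| Weeks 4 and 8 | 84 − 28 = 56 | 52 to 60 |

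**Averages, under an assumption.** If visit days were uniform and independent over the windows, the mean would be 4.07 uncovered days and 2.96 overlap days, and 35 of 729 patterns (4.8%) would leave no gap. The documents give no visit-day distribution, so these figures only illustrate.

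**Are the uncovered days days on drug?** In a 36-day interval they are the first 8 days after a new 30-tablet bottle is collected, so under daily use all 8 are. If Weeks 4 and 8 are both missed and no bottle is picked up, the patient has about 30 tablets, so at most about 30 of the 56 uncovered days can be.

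**With a look-back to the previous completed encounter** (first dose at the first follow-up), uncovered days are 0 up to the last attended encounter for every pattern.

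**The case against.** The strongest reply is that the 4-week review is not the only route into the database. Protocol 8.6.2 makes the investigator responsible for all AEs at any time in the study and says that each is assessed and recorded in the eDCF. ADRs go to the eDCF and are reported within 24 hours of the site learning of them, and fatal and other reportable events have the same 24-hour route; neither carries a look-back. This stands, and it confines the exposure mainly to not-related AEs. SAEs are included, because Protocol 8.6.2 describes SAE data as reaching the CRO through the eDCF.

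Second, the review in 8.6.2 is of documentation, not onset. An event that began on day 2 but was charted at a day-32 visit is inside the window. This also stands. What is at risk is an entry charted in the gap and not charted again at the encounter.

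Third, dose is recorded at every encounter (Appendix A, SAP Table 7.2.5), and Protocol 7.6 requires reasons for early termination to be documented. So a dose change that persists, or a discontinuation that ends participation, should be seen. A change made and reversed between encounters may not be.

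Fourth, a missed clinic visit need not be a missed encounter, since encounters may be remote, and the CRO queries missing data (Protocol 10). This reduces how often the 28-day gap arises but does not change the rule.

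On double entry, the subject-level preferred-term tables count a repeated AE once and onset dates are collected. Duplicates are therefore detectable, but no step is stated for removing them.

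A reader might infer that a fixed share of AEs is lost, for example 28/84 = 33% after a missed Week 8, or that every uncovered day is a day on drug. The documents support neither. Uncovered chart days are not lost events, and the tablet supply limits days on drug when pick-ups are missed as well.

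**Conclusion.** The point holds as a mismatch between a stated collection rule and the period that the safety tables report. The maxima (8 days between two in-window encounters, 12 in total) follow from the windows alone. The 28 days for a missed Week 8 assume nominal timing of the other encounters and no catch-up review. At exact 28-day spacing there is no gap. The direction is possible under-recording of not-related AEs and interim dose changes; its size in events cannot be derived from the documents. Overlap of up to 8 days in total could push event-level counts the other way.

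The weight is minor to moderate. Safety is an additional, descriptive objective in a single-arm study, and the primary and secondary endpoints are unaffected. A reader might take this as a failure of safety surveillance as a whole. The any-time duty and the 24-hour routes do not support that.

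**What to change.** In Protocol 8.6.2, 7.3, 7.4, 7.5 and the matching eDCF items, replace the 4-week look-back with: since the previous completed encounter (since first dose at the first follow-up encounter). Events still open from an earlier encounter are updated, not entered again.

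The SAP describes much of the follow-up in the past tense, so collection may already be complete. In that case, query sites for chart-documented AEs and dose changes wherever completed encounters, or first dose and the first completed follow-up, are more than 28 days apart. State in the SAP that event-level tables are de-duplicated by the onset date already captured (P4_i_1 and P5_i_1 in the listings).

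The cost is a wording change or one targeted query, with slightly more chart review at sites. Reported AE frequency may rise slightly. The safety denominator does not change and no clinical rule is affected. The change closes gaps up to the last attended encounter only.

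### A non-fatal SAE that the site judges Not Related, and that is not otherwise reportable, has no site reporting deadline: its only clock starts when the CRO receives eDCF data

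*Protocol*

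**What the plan says.** Protocol 8.6.2 describes two routes.

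- **ADRs.** "Each AE that meets the definition of ADR will be recorded in the Adverse Events page of the eDCF" and is also documented on a separate "Adverse Drug Reaction" form, a "form to be reported within 1 working day (24 hours) of learning of the event and proactively reported to the Almirall LLC, CRO Safety Team". The trigger is learning of the event. Section 8.6.1 defines an ADR broadly, as any AE, serious or not, for which causality cannot be excluded.
- **SAEs as such.** The sentence begins "Upon receipt of SAE data by the study CRO (collected as part of eDCF), they will be reported within 1 working day (24 hours" and goes on "of learning of the event to the sponsor regardless of its relationship to the study treatment". The trigger is arrival of eDCF data at the CRO.

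On when those data are entered, 8.6.2 says that AEs go on the "Adverse Events page of the eDCF, per study schedule of events (Appendix A", and that after each encounter "the Site Investigator will evaluate the last 4-weeks of documentation (in subject medical charts) to report AEs". Appendix A places the follow-up encounters at Weeks 4, 8 and 12, each with a window of 4 days either side.

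Section 8.6.2 also applies the limit of 1 working day from learning of the event to pregnancies, to all events with a fatal outcome, and to a list that includes overdose, medication error, off-label use and lack of effectiveness, whether or not an ADR occurred.

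The visit sections (7.3, 7.4 and 7.5) ask the site for "AEs (incl. SAEs) related to or possibly related to sarecycline". Section 8.6.2 and the AE row of Appendix A carry no such restriction.

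**The concern.** The protocol's stated aim is that every SAE reaches the sponsor quickly, whatever its cause. The clock it writes for SAEs cannot secure that for one class of event, because it starts only after the site has chosen to enter the data, and nothing says when the site must do so. A hospitalization or life-threatening event that the site calls Not Related therefore carries no site deadline, while lack of effectiveness carries one of 1 working day.

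The call of Not Related is first made by the site alone, and prompt sponsor review is the natural check on it. Delay weakens that check in an open, single-arm cohort that admits children from age 9. What is at stake is the timeliness of safety oversight. No endpoint estimate depends on it.

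**Working it through.** The plan gives no figure for reporting delay, so there is none to reproduce. The check has two parts: which events have no site deadline, and how long such an event could wait.

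**Which events are left without a site deadline**

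1. Start with all SAEs (8.6.1).
2. Remove those whose causality cannot be excluded. They are ADRs and take the 1-working-day route.
3. Remove fatal events, and those that are also a listed reportable event such as an overdose or medication error (8.6.2). Pregnancy has its own clock.
4. What remains is a non-fatal SAE positively judged Not Related and not otherwise reportable. No section of the protocol sets a time for the site to send it, or to complete the eDCF after an encounter.

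The other safeguards do not supply one. Section 9 (prompt reporting by the CRO lead) and Section 11 (checking of incoming AE data) act on data already received. Section 10 provides routine telephone and email contact with sites but no SAE deadline. The Safety Reporting Plan is cited in 8.6.2 only for ADR details and is not among the documents.

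**How long such an event could wait**

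Inputs: nominal encounters at days 28, 56 and 84 after the index date (day 0), window ±4 days (Appendix A). Assume that the site learns of the event at once and enters it only at the next scheduled encounter.

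| Interval | Shortest (days) | Longest (days) |
|---|---|---|
| Index date to Week 4 | 28 − 4 = 24 | 28 + 4 = 32 |
| Week 4 to Week 8 | (56 − 4) − (28 + 4) = 20 | (56 + 4) − (28 − 4) = 36 |
| Week 8 to Week 12 | (84 − 4) − (56 + 4) = 20 | (84 + 4) − (56 − 4) = 36 |

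- Longest wait: 32 days in the first interval, 36 days in each later one.
- Average wait if onset is uniform over a nominal 28-day interval: 28 / 2 = 14 days.
- One missed encounter: from the index date to the late edge of Week 8, 56 + 4 = 60 days; from the early edge of Week 4 to the late edge of Week 12, (84 + 4) − (28 − 4) = 64 days. SAP 6.10 expects missed visits and does not count them as deviations.

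The unspecified time to complete the eDCF, and the CRO's own 1 working day, come on top.

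Read literally, the 4-week chart review is also shorter than the longest intervals: it leaves 32 − 28 = 4 days or 36 − 28 = 8 days unreviewed.

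**The case against.** The strongest reply is that the gap is narrow and the delay is a worst case. The broad ADR definition puts every SAE of uncertain cause on the fast route, and Not Related requires good reasons to rule causality out. Sites are in regular contact with the CRO, and nothing bars early eDCF entry. All of this stands. It limits how many events are affected, but it gives the remaining ones no deadline.

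Four stronger readings are tempting, and the documents do not support them.

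- **That only ADRs have a 1-working-day clock running from awareness.** Section 8.6.2 gives the same limit to pregnancies, fatal events and the other listed events.
- **That an unrelated SAE waits two weeks where an ADR waits one day.** The 14 days run from onset, whereas the ADR clock runs from learning of the event. If the site first hears of an event at the visit, an ADR has waited just as long. The contrast holds only when the site learns at once.
- **That the wait can reach 36 days throughout.** That applies after Week 4. The first interval allows 32.
- **That unrelated SAEs are not collected.** Sections 7.3 to 7.5 are worded restrictively, but 8.6.2 and Appendix A cover all AEs and SAEs, and SAP Tables 7.4.4.2 and 7.4.4.9 include a seriousness field for not-related AEs. This is a conflict of wording to reconcile. It does not show that the data are absent.

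It might also be said that the SAE sentence mentions learning of the event and so covers the site. But the sentence opens with receipt by the CRO, so the learning it refers to is most naturally the CRO's.

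**Conclusion.** The point holds for a defined residual class: non-fatal SAEs judged Not Related and not otherwise reportable. For these the protocol states a trigger, CRO receipt of eDCF data, that leaves the site's own step untimed and so does not serve the protocol's aim of prompt reporting regardless of cause.

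The possible delay is up to about five weeks between consecutive encounters. That figure, and the average of about two weeks, rest on immediate site awareness and on entry only at the next scheduled encounter; the average also assumes uniform onset. Neither is a forecast of what sites will do, and the documents give no expected number of such events. The unavailable Safety Reporting Plan cannot be assumed either to close the gap or to leave it open.

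This is a cheap improvement to safety oversight. It does not threaten the study's endpoints.

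**What to change.** In Protocol 8.6.2, require the site to send every SAE, whatever its relatedness, to the CRO within 1 working day of learning of it, by the channel already used for ADRs. Keep the CRO-to-sponsor clock as written. This removes the wait between site awareness and CRO receipt. It cannot shorten the time before the site learns of an event.

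In the same amendment, reconcile 7.3, 7.4 and 7.5 with 8.6.2 and Appendix A, so that the visit instructions and the reporting section name the same set of AEs and SAEs.

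The cost is a short amendment with IRB approval before it takes effect (14.2), notice to up to 50 sites, and some additional expedited reports. Their number should be small, since most routes to urgency are already covered, but the documents give no rate from which to estimate it.
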